### 3.2.2 Secondary Endpoints

- Quality of life – EQ5D (a validated generic quality of life tool) over 90 days
- Compliance with stockings during admission
- Compliance with LMWH during admission

### 3.2.3 Measurement of outcomes

### 3.2.3.1 Primary outcome measure

Telephone, online or face-to-face (according to participant preference) at one week post-surgery or at discharge, and at 90 days. Proceeding to imaging at these points if there is clinical suspicion of a DVT or PE. Routine bilateral full lower limb duplex ultrasonography at between 14 days and 21 days post-operatively to capture peak VTE incidence (41,42). We expect to capture >95% of VTE since the average time-point for DVT is 7 days and PE is 21 days, with vast majority events being DVT. However, data from duplex scans outside this window will be collected and subsequently analysed.

The range of dates is to prevent restricting scanning to a single date. Routinely scanning participants only once reduces cost, and limits the time and inconvenience to the enrolled trial subjects (ethical consideration, improve recruitment and reducing dropouts and loss to follow-up). No pre-operative duplex for these same reasons and also because asymptomatic pre-operative DVTs should be accounted for by equal distribution in the two trial arms by the randomisation process. If participants are inpatients at the time of their routine bilateral full lower limb duplex ultrasonography at between 14 days and 21 days postoperatively, or if any inpatient duplex imaging is prompted by clinical suspicion, GCS will be removed prior to imaging to ensure optimum blinding of those undertaking the imaging (6). If clinical VTE is confirmed on investigation at any point within 90 days, this will be recorded. The 90 day endpoint is in line with the NHS Standard Contract for Acute Services which specifies that root cause analysis should be performed for all cases of hospital-associated VTE – defined as cases arising within 90 days of a hospital stay (40).

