## 3.2 TRIAL OUTCOME MEASURES

### 3.2.1 Primary Endpoint

VTE within 90 days { duplex ultrasound-proven new lower-limb DVT up to 90 days post-surgery (symptomatic or asymptomatic) + symptomatic PE (imaging confirmed) up to 90 days post-surgery} The 90 day endpoint is in line with the NHS Standard Contract for Acute Services which specifies that root cause analysis should be performed for all cases of hospital-associated VTE – defined as cases arising within 90 days of a hospital stay (40).

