## 7. STATISTICS AND DATA ANALYSIS

### 7.1 SAMPLE SIZE

#### 7.1.1 ORIGINAL SAMPLE SIZE- APPLICABLE UP TO JANUARY 2018

With a one-sided test at 2.5% level of significance (equivalent to a 2-sided test at 5%) the trial has 90% power to conclude that the single pharmacological intervention is non-inferior to the combined intervention (pharmacology and stockings) assuming an event rate of 6% of VTE at 90 days in the combined group and a non-inferiority margin of 3.5%, and a conservative loss to follow up (i.e. non-evaluable for the primary outcome) rate of 10%. The maximum sample size required under this group sequential design, including allowance for loss to follow up, is a total of 2236.

We assume that the standard of care gives a VTE at 90 days proportion of 6%. Historically, we believe the systematic review supports an untreated rate of at least 15%. We have set the non-inferiority margin at 3.5% (i.e. a pharmacological alone rate under the null hypothesis of not more than 9.5%). We think this is justifiable on the grounds that clinicians would not tolerate more than a 3.5% absolute deterioration in VTE event rate over combination therapy, and that it preserves  $(9-3.5)/(15-6)$  or  $5.5/9$  i.e. 61% of the established treatment effect over no intervention (greater than the 50% minimum usually required by regulatory authorities for non-inferiority studies). At 90% power and using a one-sided 2.5% level of significance (equivalent to a two-sided 5%) level we would need to randomise 1936 participants in a fixed sample approach. We prefer to adopt a group sequential approach, giving 4 equally spaced formal interim analyses for efficacy (at 25%, 50%, 75% and a final analysis at 100% of the information) and one formal interim analysis for futility at 50% information. This flexibility to stop early on either efficacy or futility only marginally increases the maximum sample size to 2012 (4% increase, using East 6.3, Cytel Corporation 2014), a flexibility which is useful given the quality, relevance and uncertainty of the evidence base informing the sample size assumptions. If we conservatively allow for 10% loss to follow up, we would need to randomise no more than 2236 in total.

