#### 7.1.2 REVISED SAMPLE SIZE (APPLICABLE AFTER JANUARY 2018)

Due to the observed low event rate it was decided to abandon the group sequential design. It was clear from the blinded (aggregate) data that the overall population, subdivided by risk of primary outcome into 4 subpopulations by VTE risk crossed with age. i.e. Subpopulation #1 <65 years,

moderate risk of VTE; subpopulation #2 <65 years, high risk of VTE; subpopulation #3 ≥ 65 years at moderate VTE risk; subpopulation #4 ≥ 65 years at high VTE risk. ( With around 250 randomised overall in subpopulation 1 (<65, moderate VTE risk) with zero expected events (0 events observed in the first 180 randomised to Dec 2017), very few events in subpopulation 2 (<65, high VTE risk; around 750 randomised to Dec 2017, observed event 3/510 or 0.6% in the first 510 randomised); virtually no-one randomised into subpopulation 3 (≥65, moderate VTE risk); only 12 randomised to Dec 2017 (this subpopulation will be reported descriptively with no further consideration of formal sample size or inference), and for subpopulation 4 (≥65, and high VTE risk) 750 in subpopulation 4 (306 randomised to Dec 2017 with 11 events observed), the study will not observe sufficient events in total or specifically in subpopulation 4 (the only subpopulation still open to recruitment) to make a re-application of the sequential design sensible.

We have considered (as at Dec 2017) the implications for the sample sizes for the 4 subpopulations, and the Table below gives the detectable non-inferiority margins for indicative sample sizes (at 90% power and a 1-sided level of significance of 2.5%):

Subpopulation	Subpopulation #	Expected number randomised	Assumed event rate	Detectable non-inferiority margin
<65, Moderate	1	258	0.1%	1.30%
<65, High	2	733	0.6%	1.85%
≥65, Moderate	3	12	N/A	N/A
≥65, High	4	912	3.6%	4.0%

Note that these revised sample size calculations do not adjust for multiple comparisons; nor do they adjust for the original group sequential alpha spending (since no interim analyses took place). See Appendix 3- Rationale for Statistical Changes to the Protocol for further details.

The funder agreed to the revised sample size of 912 in subpopulation 4 in April 2018. The other 3 subpopulations (1-3) were closed to any further recruitment at this time, and we will analyse all available data in these 3 subpopulations.

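### Silent DVT to day 90 is in the primary endpoint but is visible only on one routine scan, and the protocol does not say which scan days make a negative participant evaluable

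*Protocol*

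**What the plan says.** **Endpoint.** Protocol 3.2.1 counts duplex-proven "new lower-limb DVT up to 90 days post-surgery (symptomatic or asymptomatic") together with imaging-confirmed symptomatic PE to day 90.

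**Ascertainment.** Sections 3.2.3.1 and 6.3 plan one routine bilateral duplex for every randomised participant, at days 14 to 21. At the one-week (or discharge) and day-90 contacts, imaging follows clinical suspicion only. Section 3.2.3.1 expects to capture more than 95% of VTE and puts the average time of DVT at 7 days. It then adds: "However, data from duplex scans outside this window will be collected and subsequently analysed".

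**Evaluability.** Section 7.1.1 allows for a "conservative loss to follow up (i.e. non-evaluable for the primary outcome) rate of 10" per cent. Section 7.2.1 expects fewer than 10% missing primary outcomes and plans multiple imputation under missing at random as a robustness check. Section 7.2.2 refers the revised analysis to SAP V2.0, which was not available for this review.

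**Revised size.** Section 7.1.2 reports, for participants aged 65 or over at high risk (subpopulation 4), "306 randomised to Dec 2017 with 11 events observed". It assumes a 3.6% rate and gives a 4.0-point detectable margin for 912 randomised, with no stated allowance for non-evaluable participants.

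**The concern.** The endpoint as worded covers more than the follow-up can observe. A silent DVT that forms after the routine scan, or in someone never scanned, will not be found. That makes the status of the scan decisive for anyone with no symptomatic event, and the protocol leaves that status open. The sentence on out-of-window scans sets no earliest day. On the protocol's own timing, a negative scan in the first days after surgery cannot rule out a silent DVT that forms later. Nothing states whether such a scan settles the outcome, is supplementary, or leaves the person missing.

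The direction of the possible error matters in a non-inferiority trial. If people without an informative scan were scored as event-free because the day-90 contact was negative, silent events would be lost in both arms. The absolute difference would shrink and non-inferiority would be easier to declare. The trial is also open, so scan attendance could in principle differ by arm.

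**Working it through.** **1. The plan's own figures.** Inputs: "at 90% power and a 1-sided level of significance of 2.5" per cent, a 3.6% rate in both arms, 912 randomised 1:1 (456 per arm). With unpooled variance and z-values 1.960 + 1.282 = 3.242:

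- Standard error of the difference = √(2 × 0.036 × 0.964 / 456) = 0.01234.
- Detectable margin = 3.242 × 0.01234 = 0.0400, i.e. the stated 4.0 points.
- The same formula with the inputs of 7.1.1 (6% and 3.5 points) gives 968 per arm, or 1936, as stated. There, 2012 / 0.90 = 2236, so the first calculation does carry its 10% allowance.

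The 912 therefore reproduces only if every randomised participant is evaluable.

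**2. What 10% non-evaluable does to 912.** With 456 × 0.90 = 410.4 per arm, the standard error is 0.01300. The detectable margin becomes 3.242 × 0.01300 = 4.22 points. Power at 4.0 points is Φ(0.04 / 0.01300 − 1.960) = 86.8%.

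**3. Where the 3.6% comes from.** 11 / 306 = 3.59%, and 3 / 510 = 0.59% for those under 65 at high risk. Both use participants randomised as the denominator. Section 7.1.2 does not say how many of them had been scanned.

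**4. Conditional effect of scoring unscanned people as event-free.** Let u be the share without a valid scan and a the share of events that only the routine scan finds. The protocol gives neither, so both are assumptions. If u is equal in the two arms, each arm's rate, and so the difference, is multiplied by 1 − u × a. Take true rates of 7.6% (LMWH alone) and 3.6% (combined), so that the true difference equals the 4.0-point margin and the correct error is 2.5%. With d the observed difference and SE its standard error at 456 per arm, the error is Φ((0.04 − d) / SE − 1.960).

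| u | a | Rates scored | d (points) | SE | One-sided error |
|---|---|---|---|---|---|
| 5% | 50% | 7.41% v 3.51% | 3.90 | 0.01499 | 2.9% |
| 5% | 100% | 7.22% v 3.42% | 3.80 | 0.01481 | 3.4% |
| 10% | 50% | 7.22% v 3.42% | 3.80 | 0.01481 | 3.4% |
| 10% | 100% | 6.84% v 3.24% | 3.60 | 0.01444 | 4.6% |

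Because 7.2.1 expects fewer than 10% missing, the last row is about the ceiling if the missingness in that section includes unscanned people and is equal in the two arms. Larger values need stronger assumptions: 8.5% at u = 20% and a = 100%, or 9.9% if 15% (LMWH alone) and 5% (combined) are unscanned with a = 100%.

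**5. If the planning rate is itself diluted.** At u = 10%, the rate underlying 11 / 306 would be 3.59 / 0.95 = 3.8% (a = 50%) to 3.59 / 0.90 = 4.0% (a = 100%).

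**The case against.** A reader might infer that the protocol scores unscanned or early-scanned people as VTE-free. It does not. Section 7.1.1 has a non-evaluable category, 7.2.1 provides for missing outcomes with imputation, and SAP V2.0 may hold a derivation rule. A reader might also infer that a negative scan on day 3 counts the same as one on day 18. Section 3.2.3.1 says only that out-of-window data are analysed, and 6.3 still requires the day 14 to 21 scan for everyone randomised, so an early scan done on suspicion does not replace it by design. Late scans are not a fault in themselves: up to day 90 they fit the endpoint.

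Nor do the per-randomised rates in 7.1.2 fix the denominator of the final analysis. They are blinded planning counts. The single scan is a reasoned choice, explained by cost, burden and retention in 3.2.3.1 and supported by patient input in 9.7. No text suggests that scan attendance differs by arm, so the 9.9% is an illustration only.

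All of this stands, and it limits the point to an unresolved definition. It does not remove it. Imputation helps only once someone is classed as missing, and the protocol does not make that step for people without an informative scan. The endpoint wording and the open-ended scan sentence are protocol text.

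**Conclusion.** The point holds as a gap in the endpoint definition, not as a demonstrated bias. The protocol promises silent DVT to day 90, observes it once, admits scans at other times without an earliest day or a stated role, and does not say who is evaluable. If people without a valid scan were scored as event-free, one-sided error in subpopulation 4 would be about 2.9 to 4.6% instead of 2.5%. That range rests on an assumed 5 to 10% without a valid scan, 50 to 100% of events found only by scan, equal shares in the two arms, and a scoring rule the protocol does not state.

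Separately, and without any scoring assumption, the 912 has no room for non-evaluable participants, although 7.1.1 allowed 10%. The change is worth making because the ambiguity bears on the primary endpoint and any resulting error would favour non-inferiority.

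**What to change.** 1. In 3.2.1 and 3.2.3.1, describe the endpoint as asymptomatic DVT on the routine duplex plus symptomatic VTE to day 90.
2. Accept a negative routine scan as no VTE only if it was done on or after day 14, late scans up to day 90 included, with no VTE by the day-90 contact.
3. Count any confirmed VTE to day 90 as an event, whenever it is found.
4. Treat all other event-free participants as missing and carry the imputation of 7.2.1 into the revised analysis. Do not simply exclude them: symptomatic cases would stay in while unscanned event-free people dropped out, so evaluability would depend on outcome and rates would be pushed up. For the same reason, impute the absent scan result given no symptomatic VTE, not the whole endpoint.
5. Add a sensitivity analysis limited to scans at days 14 to 21.
6. In 7.1.2, say whether the 3.6% is per randomised or per evaluable participant, and restate what 912 delivers after losses.

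Cost: wording and one derivation rule, provided the date of each scan is recorded. The real price is fewer observed outcomes. The revised size does not cover this: with 10% non-evaluable, 912 gives about 86.8% power at 4.0 points, or a 4.22-point detectable margin. If SAP V2.0 already sets these rules, the protocol needs only to be aligned with it.

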### 3.2.3.2 Secondary outcome measures

Generic quality of life will be assessed at baseline, upon discharge and at follow-up (both 14-21 days and 90 days) using the EQ-5D. EQ-5D is widely used and well validated, and is currently employed as part of the routine collection of Patient Reported Outcome Measures (PROMs) for the NHS in England (43).

Compliance with stockings will be addressed; participants will be issued with a VTE diary where they can document their GCS use, as well as any adverse outcomes related to GCS or LMWH use.

Compliance with LMWH will be assessed by review of the participant's medication chart by the local research nurse or study coordinator.

Mortality will be recorded however, it is anticipated that this will be very low.

### *3.2.3.3 Safety outcome measures*

GCS-related complications, bleeding complications and adverse reactions to LMWH will be determined by review of medical notes and participant-reported comments in their VTE diary.

## **4. PARTICIPANT ENTRY**

### **4.1 PRE-REGISTRATION EVALUATIONS**

The target population is adult (aged  $\geq 18$  years) elective surgical inpatients in secondary and tertiary NHS hospitals in the UK assessed as being at moderate or high risk of VTE. This target population is described based on their risk of VTE. There is an established VTE risk assessment tool which has been produced by the Department of Health (38), based on the NICE guidelines (1), and is mandated and in widespread use (44).

#### **4.1.1 Screening and Participant identification**

Adult patients presenting to the surgical wards related to a number of surgical specialties for elective surgery at the recruiting centres will be screened for eligibility. The trial will be pragmatic and include 'all comers' in terms of surgical specialty and operation type, which would allow the results of the trial to be maximally generalizable and externally valid, in addition to facilitating recruitment.

Patients will be admitted to hospital for their elective surgery, and are VTE risk assessed by the doctor or nurse during the admission process in accordance with NICE guidelines and the Department of Health. Risk assessment will identify patients as 'low risk' or 'not low risk' for a VTE.

If a patient is identified as 'not low risk' for VTE and 'not at high risk' for bleeding (i.e. can safely receive LMWH) the clinical team will flag patient to research nurse who will approach patient and will offer them an information leaflet about the trial. Participants will only be approached by the research team when they have given permission for this to happen via a member of their direct care team. Patients will be given an appropriate time period to consider participation. Written consent will be obtained from those patients who agree to participate..

Information about the study may be sent by post or given (for example in the outpatient clinic) potential participants by the direct care team prior to admission. This will allow potential participants to consider being involved in the study prior to their admission for surgery. This information will highlight that eligibility for the trial would be assessed following VTE risk assessment and not all patients would be eligible for the trial.

At each recruiting centre, a log of all screened patients will be kept. Basic demographic data and reasons for non-eligibility will be recorded.

Those who consent will be registered on the web-based data entry system which is maintained by CHaRT (The Centre for Healthcare Randomised Trials, NIHR registered Clinical Trials Unit #7, University of Aberdeen), and their eligibility for the trial confirmed. The randomisation will be web-based hosted at CHaRT, using a minimisation algorithm incorporating centre, moderate or high risk of VTE and gender, and in addition incorporate a random element. Although the trial is open (unblinded) every effort will be made to manage the patients and assess the study outcomes without any knowledge of the randomly assigned treatment being allowed to create any bias.

The VTE risk assessment tool (or the Trust equivalent based on this form) will be used for all patients (Appendix 2). The moderate and high-risk populations for inclusion in this trial are clearly defined according to this risk assessment tool. As patients will already be assessed as part of their admission process (with a target of >95% compliance under the NHS Contract), no additional VTE risk assessment will need to be undertaken for recruitment as part of the trial. Furthermore, no additional training is required for the individual who is undertaking the risk scoring.

## 4.2 INCLUSION CRITERIA

- Elective surgical inpatients assessed as being at moderate or high risk of VTE according to the widely-used UK Department of Health VTE Risk Assessment for Venous Thromboembolism (or the Trust equivalent based on this form) (38) (Appendix 2, based upon the NICE recommendations (1)).\*
- Able to give informed consent to participate in the trial after reading the patient information documentation
- Age  $\geq 18$  years\*

Patients who cannot speak / understand English will be eligible for inclusion and informed consent will be obtained with assistance from translation services as per standard clinical practice. In view of the lack of cross-cultural validation for quality of life tools, only VTE outcome data will be collected.

Patients involved in current or recent research may be included provided that the research does not impact (either positively or negatively) on their risk of VTE, or a contraindication or interaction with LMWH or GCS. Any queries should be directed to the Chief Investigator.

\*Following confirmation from the REC and the Sponsor from 20th December 2018, sites will continue to recruit only patients assessed as being at high risk of VTE and aged  $\geq 65$  years. Recruitment of those  $<65$  and at moderate or high VTE risk is considered closed. Further details can be found in Appendix 3.

### 4.3 EXCLUSION CRITERIA

- Contraindications to low molecular weight heparin (LMWH)
- Contraindications to GCS, including peripheral arterial disease, stroke patients, individuals undergoing lower limb surgery
- Documented or known thrombophilia or thrombogenic disorder
- Individuals requiring therapeutic anticoagulation
- Previous venous thromboembolism (VTE)
- Patients having intermittent pneumatic compression (IPC) beyond theatre and recovery
- Patients requiring inferior vena cava (IVC) filter
- Pregnancy (female participants of reproductive age will be eligible for inclusion in the trial, subject to a negative pregnancy test prior to randomisation, and again on the day of surgery if there is a possibility of pregnancy since the last test)
- Patients requiring thromboprophylaxis to be extended beyond discharge
- Application of a cast or brace in theatre

### 4.4 CHANGE OF STATUS / WITHDRAWAL PROCEDURES

Participants will remain in the trial unless they choose to withdraw consent or if they are unable to continue for a clinical reason. All changes in status with the exception of complete withdrawal of consent will mean the participant is still followed up for all trial outcomes wherever possible. All data collected up to the point of complete withdrawal will be retained and used in the analysis.

## 5. ADVERSE EVENTS

The GAPS trial involves procedures for the management of patients at moderate and high risk of VTE which are well established in clinical practice. Adverse effects may occur during or after any type of surgery.

### 5.1 DEFINITIONS

**Adverse Event (AE):** any untoward medical occurrence in a patient or clinical trial participants.

**Serious Adverse Event (SAE):** any untoward and unexpected medical occurrence or effect that:

- **Results in death**
- **Is life-threatening** – *refers to an event in which the participants was at risk of death at the time of the event; it does not refer to an event which hypothetically might have caused death if it were more severe*
- **Requires hospitalisation, or prolongation of existing inpatients' hospitalisation**
- **Results in persistent or significant disability or incapacity**
- **Is a congenital anomaly or birth defect**

Medical judgement should be exercised in deciding whether an AE is serious in other situations. Important AEs that are not immediately life-threatening or do not result in death or hospitalisation but may jeopardise the participants or may require intervention to prevent one of the other outcomes listed in the definition above, should also be considered serious.

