#### 5.3.1 Non-Serious AEs

The adverse events listed below are expected to be related and should be reported:

- GCS-related complications during admission (e.g. discomfort, skin breaks, skin ulcers, skin necrosis, blistering of the skin, rash, limb ischaemia)
- Bleeding complications during admission or within 24 hours of discharge
- Adverse reaction to LMWH during admission (e.g. rash or skin change, allergic reaction, thrombocytopenia, abnormal liver enzyme tests)

**Please note this is not an exhaustive list, if you suspect an event is related to treatment please contact the Trials Unit.**

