### 5.3.2 Serious AEs

All SAEs should be reported. An SAE form should be completed and entered into the trial website within 24 hours. However, hospitalisations for elective or urgent treatment of a pre-existing condition do not need reporting as SAEs. In the event that the trial website is not available the Trial Manager should be notified by telephone, fax or email.

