### 5.3.3 Reporting responsibilities of the CI

When an SAE form is uploaded onto the trial website, the Trial Manager will be automatically notified and will notify the Sponsor within 24 hours of receiving the signed SAE notification. The Sponsor will review all reported SAEs. A Sponsor cannot downgrade an assessment from the PI or CI. Any disparity will be resolved by further discussion between these parties.

If all the required information is not available at the time of reporting, the Investigator must ensure that any missing information is provided as soon as this becomes available. It should be indicated on the report that this information is follow-up information of a previously reported event.

All SAEs should be reported to the research ethics committee where in the opinion of the Chief Investigator, the event was:

- 'related', i.e. resulted from the administration of any of the research procedures; and

- 'unexpected', i.e. an event that is not listed in the protocol as an expected occurrence

Reports of related and unexpected SAEs should be submitted within 15 days of the Chief Investigator becoming aware of the event, using the NRES SAE form for non-IMP studies. The Chief Investigator must also notify the Sponsor of all SAEs.

Local investigators should report any SAEs as required by the, Sponsor and/or Research and Development Office.

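### The SAE definition in Protocol 5.1 requires an event to be unexpected, so listed complications can miss SAE reporting; separately, 4.2 as worded drops all non-VTE data for participants who cannot speak or understand English

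*Protocol*

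**What the plan says.** **SAE rules.** Protocol 5.1 defines an SAE as "any untoward and unexpected medical occurrence or effect that" leads to one of the usual serious outcomes, such as death, threat to life, or new or prolonged hospitalisation. It then asks for medical judgement in other situations and says that "Important AEs that are not immediately life-threatening or do not result in death or hospitalisation" may also count as serious if they put the participant at risk or need intervention.

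Section 5.3.1, headed as covering non-serious events, introduces its list with "The adverse events listed below are expected to be related and should be reported". The list includes "GCS-related complications during admission (e.g. discomfort, skin breaks, skin ulcers, skin necrosis, blistering of the skin, rash, limb ischaemia" and "Bleeding complications during admission or within 24 hours of discharge", as well as reactions to LMWH.

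Section 5.3.2 says "All SAEs should be reported", with a form entered within 24 hours. Section 5.3.3 sends SAEs to the ethics committee if they are both related and unexpected, where unexpected means "an event that is not listed in the protocol as an expected occurrence".

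**Language rule.** Section 4.2 makes patients who cannot speak or understand English eligible, with translation support for consent, and adds: "In view of the lack of cross-cultural validation for quality of life tools, only VTE outcome data will be collected".

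**The concern.** Seriousness and expectedness are different properties. Seriousness decides whether an event is reported quickly and reviewed. Expectedness normally decides only which serious events go further, to the ethics committee. Section 5.1 merges the two, and the events that the protocol lists as expected are the known harms of the two prophylactic measures under study.

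What is at stake is safety oversight while the trial runs. The protocol makes the adverse-effect profile of stockings and LMWH an objective (Trial Summary; 1.3), and its background section says that any benefit of stockings must be weighed against their harms (1.1). If the gravest listed complications are handled as non-serious, the sponsor and the iDMC chair may not see them promptly.

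The language rule raises a separate question of completeness. Its reason concerns one type of instrument, but its wording covers everything except VTE.

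**Working it through.** No arithmetic applies: neither point depends on a rate, margin or sample size. The check sets the sections side by side.

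**SAE definition**

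1. Under 5.1 an event must be unexpected to be an SAE.
2. The protocol explains *unexpected* only in 5.3.3: not listed in the protocol as expected.
3. Section 5.3.1 lists bleeding, skin necrosis, limb ischaemia and LMWH reactions as expected.
4. Taken together, a listed bleed that prolongs the stay or threatens life fails the 5.1 definition, although it meets a seriousness criterion.
5. The 24-hour form in 5.3.2 applies to SAEs. Notification of the sponsor and its review (5.3.3) start from an uploaded SAE form. The report of related SAEs to the iDMC chair (9.5) also depends on SAE status. An event that fails at step 4 can miss all three.
6. Section 5.3.3 shows that the word is misplaced in 5.1. If every SAE were already unexpected, the second test in 5.3.3 would remove nothing. That section makes sense only if expected SAEs exist.
7. The sentence on important events in 5.1 carries no condition of unexpectedness, but it is written for events short of death, immediate threat to life or hospitalisation. Events with those outcomes rest on the main definition. The less grave event therefore has the clearer route to being called serious.
8. The list in 5.3.1 is limited in time: to the admission, plus 24 hours after discharge for bleeding. The conflict is clearest inside those windows. The text does not settle whether the same complication occurring later counts as expected.

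**What still captures these events.** Section 5.3.1 requires listed events to be reported. Section 3.2.3.3 takes stocking complications, bleeding and LMWH reactions from the medical notes and the participant diary, whatever their SAE status. Sections 6.2 and 6.4 collect adverse and serious adverse events at follow-up. The definition therefore costs serious classification and expedited reporting, and it does not remove the event from the record.

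**Language rule**

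| Item | Source in the protocol | Needs a validated quality-of-life tool? | Kept under 4.2 as worded? |
|---|---|---|---|
| VTE | 3.2.3.1 | No | Yes |
| EQ-5D | 3.2.3.2 | Yes | No |
| LMWH compliance | Medication chart, 3.2.3.2 | No | No |
| Stocking compliance | Diary, 3.2.3.2 | No | No |
| Mortality | Recorded, 3.2.3.2 | No | No |
| Safety outcomes | Notes and diary, 3.2.3.3 | No | No |

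The stated reason justifies one of the five exclusions. The rule also conflicts with 5.3.2 and with the event collection in 6.2 and 6.4, none of which makes an exception for language.

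**The case against.** The best defence is that the intent can be recovered. Section 5.3.1 can be read as saying how listed events are reported when they are not serious, without saying that they can never be serious. Section 5.3.2 asks for every SAE and names one exemption, for treatment of a pre-existing condition, and none for listed events. Section 5.3.3 presupposes expected SAEs, 9.5 applies no test of unexpectedness, and sites in doubt are told to ask (5.2; 5.3.1). On the language rule, the sentence is about quality-of-life tools, and no reporting section exempts anyone.

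This defence shows what was probably meant. It does not repair the definition that a site must apply, because the duty in 5.3.2 covers only what 5.1 calls an SAE. Likewise, 4.2 states a plain rule that the other sections contradict without overriding.

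A reader might infer more than the document supports:

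- *That the SAE definition takes serious bleeding or skin necrosis out of the safety comparison.* It does not: 3.2.3.3 and 5.3.1 keep those events whatever their SAE status.
- *That limb ischaemia needing intervention would not be an SAE.* The sentence on important events in 5.1 largely catches it.
- *That participants without compliance data cannot be placed in the per-protocol set.* Section 7.2.1 leaves that set to be specified and gives primacy to intention to treat, so the protocol alone cannot show this.
- *That the number affected by 4.2 can be estimated.* The protocol gives nothing on the share of such participants.
- *That leaving out stockings trades VTE against bleeding.* Both arms receive LMWH, so the protocol does not set up that trade.

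**Conclusion.** Both points hold as conflicts of wording with a practical consequence. First, 5.1 contradicts 5.3.2 and 5.3.3 on expectedness. Read with the list in 5.3.1, a listed complication that causes death, threat to life or prolonged hospitalisation can be classed as non-serious and miss the 24-hour report, sponsor review and the related-SAE report to the iDMC chair. It stays a reportable adverse event and a safety outcome. Second, 4.2 excludes more than its reason supports and conflicts with 5.3.2, 6.2 and 6.4. As worded, it is the only one of the two rules that takes safety, compliance and mortality data out of the trial's record.

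Neither effect can be sized. The first depends on how literally sites apply 5.1 and on how many serious listed events occur. The second depends on the unstated number of participants who cannot speak or understand English. The wording conflict itself is certain. The change is worth making because these are stated rules that give a worse result when followed, which goes beyond missing detail.

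**What to change.** Three changes of wording:

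1. In 5.1, delete the requirement of unexpectedness from the SAE definition, and keep expectedness only in 5.3.3 as the test for ethics reporting.
2. In 5.3.1, state that a listed event meeting any seriousness criterion is reported as an SAE under 5.3.2.
3. In 4.2, limit the exception to EQ-5D, so that all other outcome, safety, compliance and mortality data are collected from participants who cannot speak or understand English.

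The cost is a short note to sites, a few more SAE forms and a few more data items. Version 3.0 is dated 3 December 2018 and Appendix 3 has recruitment and follow-up of subpopulation 4 running until April 2019, so the change could still take effect during the trial. For participants already enrolled, the items that come from medical notes and medication charts do not depend on the participant's language.
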